1.0 Study Summary

Study Title	Comparison of postoperative analgesic efficacy of femoral	
	nerve block with IPACK versus femoral and popliteal sciatic	
	nerve block in patients undergoing arthroscopic anterior	
	cruciate ligament reconstruction.	
Study Design	Prospective study	
Primary Objective	The primary objective of the study is to compare the	
	analgesic efficacy of FNB with IPACK versus FNB with	
	sciatic nerve block in patients undergoing ACL repair by	
	monitoring postoperative pain scores.	
Secondary	The secondary objective is to show a decreased incidence of	
Objective(s)	adverse effects including motor blockade with IPACK	
	compared to sciatic nerve block and to demonstrate that it is	
	technically less challenging by showing a decreased time	
	required for performance of the block.	
Research	Patients will receive up to 20 mL of 0.5 % ropivacaine with	
Intervention(s)/	epinephrine 1:200,000 and 0.2 mg/ml of dexamethasone for	
Investigational	FNB-AC and up to 20 mL of 0.5% ropivacaine with	
Agent(s)	epinephrine 1:200,000 and 0.2 mg/ml of dexamethasone for	
	sciatic nerve block or posterior knee capsular infiltration.	
IND/IDE #	N/A	
Study Population	Patients undergoing elective anterior cruciate ligament	
	reconstruction.	
Sample Size	50	
Study Duration for	Total of 2 weeks.	
individual		
participants		
Study Specific	IPACK – infiltration of the posterior knee capsule	
Abbreviations/	FNB - Femoral nerve block	
Definitions	PACU – post-anesthesia care unit	
	POD – post-op day	

2.0 **Objectives**

- 2.1 The primary objective of the study is to compare the analgesic efficacy of FNB with IPACK versus FNB with sciatic nerve block in patients undergoing ACL repair by monitoring postoperative pain scores.
- 2.2 The secondary objective is to show a decreased incidence of adverse effects including motor blockade with IPACK compared to sciatic nerve block and to demonstrate that it is technically less challenging by showing a decreased time required for performance of the block.
- 2.3 We hypothesize that FNB with IPACK provides the same analgesic efficacy as FNB with sciatic block while avoiding the motor blockade associated with sciatic nerve block.

3.0 Background

- 3.1 Anterior cruciate ligament reconstruction is one of the most common orthopedic surgical procedures performed on an outpatient basis.1 The ability to effectively discharge these patients is primarily determined by the efficacy of postoperative pain control. Regional anesthetic techniques are commonly used to provide postoperative analgesia as they provider superior analgesia when compared to opioids and have also been shown to facilitate same day, outpatient discharge home.2 Various regional techniques have been used, generally combining blockade of the femoral and sciatic nerve to provide analgesia of the knee and surrounding structures. Performance of the sciatic nerve block can be technically challenging and time consuming. One alternative to sciatic nerve block is infiltration of the posterior knee capsule (IPACK) under ultrasound guidance. Results with IPACK in adults for posterior knee joint analgesia in patients undergoing total knee arthroplasty have been comparable to sciatic nerve block. Furthermore, IPACK is technically less challenging as it is only infiltration of the knee capsule below the division of the sciatic nerve, without targeting for nerves, and is not associated with motor block.3
- 3.2 The aim of the current study is to determine if the analgesic efficacy of IPACK is similar to sciatic nerve block thereby reducing the side effects involved with sciatic nerve block as well as the technical challenges of performing the block.

4.0 Study Endpoints

- 4.1 The time for performance of the block (FNB plus sciatic versus FNB plus IPACK).
- 4.2 Intraoperative opioid (fentanyl) and inhalational anesthetic agent (sevoflurane) requirements.
- 4.3 Pain scores and opioid requirements in the PACU.
- 4.4 Degree of sensory and motor block in phase I (PACU) and phase 2 recovery.
- 4.5 Post-discharge opioid requirements and pain scores (pain diary).
- 4.6 Duration of subjective postoperative sensory and motor blockade.

5.0 Study Intervention/Investigational Agent

5.1 Study subjects will receive up to 20 mL of 0.5% ropivacaine with epinephrine 1:200,000 and 0.2 mg/ml of dexamethasone for FNB and up to 20 mL of 0.5% ropivacaine with epinephrine 1:200,000 and 0.2 mg/ml of dexamethasone for sciatic nerve block under ultrasound guidance or posterior knee capsular infiltration under ultrasound guidance (IPACK), the total dose not to exceed 3 mg/kg of ropivacaine.

5.2 Both the FNB and sciatic nerve blocks are considered standard of care at NCH. The IPACK is not currently performed at NCH.

6.0 **Procedures Involved***

- Following informed consent, patients will be randomized into one of 6.1 the two groups. Intraoperative anesthetic care will not vary from our usual practice. Patients requiring preoperative anxiolysis will receive oral midazolam (0.3-0.5 mg/kg, maximum 20 mg) 30 minutes prior surgery or intravenous midazolam (0.05 mg/kg, maximum 2 mg) prior to transport to the operating room. Standard American Society of Anesthesiologists' monitors will be placed. Once in the operating room, anesthesia will be induced by the intravenous or inhalational route as clinically indicated. All subjects will receive propofol (2-3 mg/kg) and fentanyl (2µg/kg). Following the induction of anesthesia, an appropriately sized laryngeal mask airway (LMA) will be placed. After the regional anesthesia time out, patients will receive the block based on the group assigned from a randomization list created by www.sealedenvelope.com. The time from the initiation of the timeout for the block until the patient has been returned to the surgical position will be noted.
- 6.2 The following demographic and surgical parameters will also be collected and recorded: patient age, gender, race/ethnicity, height, weight, ASA status, primary diagnosis, list of comorbidities, procedure date and duration, admission status, intraoperative medications and postoperative medications, PACU arrival and discharge times, discharge destination, pain scores (including recorded time), regional anesthetic time and dose, postoperative opioids consumed and time of hospital admission and discharge.
- 6.3 Group 1: Patients will receive up to 20 mL of 0.5% ropivacaine with epinephrine 1:200,000 and 0.2 mg/ml of dexamethasone for FNB and up to 20 mL of 0.5% ropivacaine with epinephrine 1:200,000 and 0.2 mg/ml of dexamethasone for sciatic nerve block under ultrasound guidance, the total dose not to exceed 3 mg/kg of ropivacaine (total volume 1.5 mL/kg of 0.2% ropivacaine). For patients who weigh less than 30 kg, the volume of the local anesthetic will be reduced to keep the total dose at \leq 3 mg/kg.

Group 2: Patients will receive up to 20 mL of 0.5% ropivacaine with epinephrine 1:200,000 and 0.2 mg/ml of dexamethasone for FNB and up to 20 mL of 0.5% ropivacaine with epinephrine 1:200,000 and 0.2 mg/ml of dexamethasone for posterior knee capsular infiltration under ultrasound guidance (IPACK), the total dose not to exceed 3 mg/kg of ropivacaine. For patients who weigh less than 30 kg, the volume of the local anesthetic will be reduced as needed to keep the total dose at \leq 3 mg/kg.

- 6.4 For intraoperative increases in heart rate or systolic blood pressure $\geq 20\%$ above the baseline, fentanyl (1 µg/kg) will be administered every 5 minutes until the heart rate is below this threshold. Prophylaxis for postoperative nausea and vomiting will include ondansetron (0.1-0.15, maximum 4 mg). At the conclusion of the procedure, all patients will receive ketorolac (0.5 mg/kg, maximum 30 mg).
- 6.5 Patients experiencing severe pain with VAS scores >7 at the surgical site will be considered as failed FNB or sciatic nerve block and will be withdrawn from the study. In the postoperative care unit, the nursing staff will be blinded to which group the patient was assigned to, reducing bias. Fentanyl (1 μ g/kg, maximum 50 μ g) will be administered every 5-10 minutes as needed until the patient's visual analogue score (VAS) score is \leq 4. VAS will be evaluated every hour until discharge. When the patients are ready for discharge and tolerating oral intake, analgesia will be changed to hydrocodone with acetaminophen, 1 tablet by mouth if needed, prior to discharge home.
- 6.6 Patients will be discharged home with postoperative pain medication to include hydrocodone with acetaminophen. Parents will be instructed to administer one tablet every 4 hours as needed when the VAS score is greater than 4. If the patient does not tolerate hydrocodone, the patient will be given the option for ibuprofen 10 mg/kg every 6 hours. Caregivers will be given a diary to record the amount of pain medication consumed, pain scores (every 4-6 hours), and the duration of motor block as reported by the patient. On postoperative day 1(or 2 for a later discharge), a member of the study team will call to collect the information for a total of 24 hours following hospital discharge. The study investigator will also contact the patients 2 weeks after the procedure to assess for any adverse events not detected during the initial data collection.

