15.0 Risks to Subjects*

- 15.1 The common side effects of ropivacaine (the numbing medication used in the nerve blocks) are injection site burning or pain and prickly feeling as the block wears off. Occasional side effects of ropivacaine are ear ringing, metallic taste, and drowsiness. Rare side effects of ropivacaine are seizures, unconsciousness, respiratory arrest, low blood pressure, irregular heartbeat, cardiac arrest, and allergic reactions including anaphylaxis. There is also potential risk for loss of confidentiality.
- 15.2 Subjects and their families will be approached about the study and consented in a private room in the pre-op area by a member of the research team. The information collected will be limited to that which is required to achieve the objectives of the study and will not be shared with anyone not directly involved in the study. Subjects will be informed of their right to refuse to participate. Subject PHI will be stored in a locked cabinet, and will be stored and maintained in password protected computer files.

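### Section 6.3's 30 kg volume-reduction trigger (both arms) and its 0.2% conversion (Group 1) do not fit the specified 0.5% ropivacaine, for which the 3 mg/kg cap limits volume in every patient under about 67 kg

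*Combined protocol and SAP*

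**What the plan says.** Sections 1.0, 5.1 and 6.3 all specify 0.5% ropivacaine, with up to 20 mL for the femoral block and up to 20 mL for the second block (sciatic in Group 1, IPACK in Group 2).

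Section 5.1 sets the limit for all subjects, with no weight condition: "the total dose not to exceed 3 mg/kg of ropivacaine". Section 6.3 repeats it in each arm. The summary in section 1.0 gives the volumes without the cap.

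Section 6.3 then adds two practical aids:

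- **Group 1 only, a volume equivalent of the cap:** "the total dose not to exceed 3 mg/kg of ropivacaine (total volume 1.5 mL/kg of 0.2% ropivacaine". No other part of the document mentions a 0.2% solution.
- **Both arms, a weight trigger.** Group 1: "For patients who weigh less than 30 kg, the volume of the local anesthetic will be reduced to keep the total dose" at or below 3 mg/kg. Group 2: "For patients who weigh less than 30 kg, the volume of the local anesthetic will be reduced as needed to keep the total dose" at or below 3 mg/kg.

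Section 10.2 admits patients aged 10 to 21 and sets no weight criterion.

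**The concern.** A weight trigger and a mL/kg conversion spare the clinician a calculation at the time of the block. They do so safely only if they are derived from the solution being injected and from the cap in force. Here neither agrees with 0.5% and 3 mg/kg. An instruction to cut the volume under 30 kg is naturally taken to mean that heavier patients may receive the full volume. Under this cap that is untrue over a wide band of weights, and the age range does not exclude patients in that band.

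What is at stake is clarity in a local-anaesthetic dose limit. Section 15.1 says: "Rare side effects of ropivacaine are seizures, unconsciousness, respiratory arrest, low blood pressure, irregular heartbeat, cardiac arrest". The point does not touch the primary endpoint, the non-inferiority test or the sample size.

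**Working it through.** **Inputs** (sections 5.1 and 6.3): concentration 0.5%; maximum 20 mL + 20 mL = 40 mL; total cap 3 mg/kg; reduction trigger 30 kg; Group 1 conversion 1.5 mL/kg at 0.2%.

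**Formulas.**
- mg/mL = 10 × percent
- cap in mL/kg = 3 ÷ (mg/mL)
- weight below which 40 mL exceeds the cap = 40 × (mg/mL) ÷ 3

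**The plan's own conversion.** 0.2% is 2 mg/mL, and 3 ÷ 2 = 1.5 mL/kg. The figure reproduces exactly for 0.2%.

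**The same conversion for the study solution.** 0.5% is 5 mg/mL, and 3 ÷ 5 = 0.6 mL/kg.

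**The 30 kg trigger.** Three derivations were tried:
- 40 mL at 0.5%: 200 mg; 200 ÷ 3 = 66.7 kg
- 40 mL at 0.2%: 80 mg; 80 ÷ 3 = 26.7 kg
- one 20 mL block at 0.5%: 100 mg; 100 ÷ 3 = 33.3 kg, although the cap covers both blocks together

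None gives 30 kg, and the documents do not say where it comes from. On the stated inputs, the weight at which the cap starts to limit the volume is 66.7 kg.

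**The band the trigger leaves out:**

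| Weight (kg) | Cap (mg) = 3 × kg | Permitted volume (mL) = 0.6 × kg | Shortfall from 40 mL (mL) | Dose if 40 mL given (mg/kg) = 200 ÷ kg |
|---|---|---|---|---|
| 30 | 90 | 18 | 22 | 6.67 |
| 40 | 120 | 24 | 16 | 5.0 |
| 50 | 150 | 30 | 10 | 4.0 |
| 60 | 180 | 36 | 4 | 3.33 |
| 66.7 | 200 | 40 | 0 | 3.0 |

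The last column is conditional. It applies only if someone gives the full 40 mL because the trigger did not call for a reduction, and does not check the dose against the cap.

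**The case against.** The governing rule is complete. The 3 mg/kg cap appears without a weight condition in section 5.1 and in both arms of section 6.3, and the volumes are upper limits. No dose above 3 mg/kg complies with the protocol at any weight, and a clinician who works out mg/kg first will be compliant. The trigger sentence names no volume and restates the cap. The one conversion shown is arithmetically right for the concentration it names. So this is an inconsistency between parts of the text, not a miscalculation. All of that stands.

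It does not remove the point. An explicit trigger at 30 kg, where the cap starts to bind at 66.7 kg, still misleads about the weights between. A conversion for a solution the trial does not use gives no help with the one it does use.

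Two stronger readings are tempting, and the documents support neither:

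- **That the protocol directs an overdose.** It does not; the cap overrides both aids.
- **That Group 1 patients could receive 7.5 mg/kg**, from 1.5 mL/kg × 5 mg/mL. The parenthesis expressly names 0.2%. The 40 mL maximum also takes over at 40 ÷ 1.5 = 26.7 kg, so that dose could arise only in patients under 30 kg, for whom the next sentence already orders reduction to 3 mg/kg or less. Reaching it would mean disregarding the concentration label, the cap and the trigger together.

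**Conclusion.** The point holds as an internal inconsistency in section 6.3 that should be corrected. With 0.5% ropivacaine and a 3 mg/kg cap, the volume limit is 0.6 mL/kg and a reduction below 40 mL is required for every patient under 66.7 kg. The explicit trigger covers only those under 30 kg, and Group 1's conversion belongs to a different concentration.

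The size of the discrepancy is certain, because it follows from the protocol's own figures. Its practical consequence is not. The documents give no weight distribution, so neither the number of patients between 30 and 67 kg nor the chance of a dosing error can be estimated. The conclusion assumes that 0.5% and 3 mg/kg are the intended values. If either is not, both aids need to be derived again from the intended one.

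A reader might also infer, because only Group 1 carries the conversion, that the arms have different dose limits. They do not: concentration, maximum volumes and cap are the same in both.

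**What to change.** In both arms of section 6.3, replace the 30 kg trigger (and in Group 1 also the 0.2% parenthesis) with one identical sentence, for example: *Total volume of 0.5% ropivacaine for both blocks not to exceed 0.6 mL/kg (3 mg/kg), maximum 40 mL; this requires a reduction below 40 mL for every patient under about 67 kg.* If another concentration or cap is intended, state it and derive the mL/kg limit and the weight threshold from it.

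The cost is a short text amendment. Sample size, schedule and data collection do not change. Section 6.2 already records weight and "regional anesthetic time and dose", so adherence to 3 mg/kg can be checked from data already planned, though only after the block has been given.

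### Apart from motor blockade, the adverse effects in objective 2.2 are undefined and have no endpoint or stated collection before the 2-week contact

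*Combined protocol and SAP*

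**What the plan says.** Section 2.2 (repeated in the summary, 1.0) sets the aim: "The secondary objective is to show a decreased incidence of adverse effects including motor blockade with IPACK compared to sciatic nerve block". Motor blockade is thus one member of a wider set, and the other members are not listed.

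Two endpoints in 4.0 bear on this aim: 4.4, "Degree of sensory and motor block in phase I (PACU) and phase 2 recovery", and 4.6, "Duration of subjective postoperative sensory and motor blockade". The rest of 4.0 covers block time, intraoperative anaesthetic and opioid use, pain scores and postoperative opioids.

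Section 6.2 opens its itemised list with "The following demographic and surgical parameters will also be collected and recorded". The list has no adverse-event item. Section 6.5 describes VAS scoring and fentanyl in the PACU. In 6.6, "Caregivers will be given a diary to record the amount of pain medication consumed", and its other two fields are pain scores and motor-block duration. The call on postoperative day 1 or 2 gathers that information for the 24 hours after discharge.

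Section 6.6 then has the investigator contact patients at 2 weeks "to assess for any adverse events not detected during the initial data collection". Section 15.1 lists ropivacaine side effects as risks, the common ones being "injection site burning or pain and prickly feeling as the block wears off". Section 17.1 gives a generic test for categorical outcomes and names no adverse-effect variable. Section 18.1 says only that the investigators monitor the study.

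**The concern.** The objective is comparative: it sets out to show a lower incidence in one arm. That requires a defined set of events, asked about in the same way and at the same times in both arms. For everything except sensory and motor block, the plan gives neither the definition nor the times.

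Two consequences follow.

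- **Under-recording.** Effects such as prickling as the block recedes, or drowsiness, would on the stated procedures first be asked about at about day 14. The only blinding stated is of PACU nursing staff (6.5). The 2-week contact has no stated blinding or standard wording, so reporting could also differ between arms.
- **A one-sided claim.** The only adverse effect collected systematically is the one that 2.3 and 3.1 expect to favour IPACK. The objective could be declared met on that effect alone, while other harms of a technique not currently performed at the site (5.2) go largely uncounted.

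**Working it through.** The check is mainly a comparison of sections. The plan gives no adverse-effect rate and no calculation for this objective.

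**1. The plan's own figure.** Section 12.2 sizes the trial on maximal pain on the day of surgery, with margin 1, SD 1.1, one-sided 5% and 90% power. I take the true difference as 0.
- Normal approximation: n = 2 × 1.1² × (1.645 + 1.282)² / 1² = 20.7, so 21 per group.
- Exact t with 22 per group: noncentrality 1 / (1.1 × √(2/22)) = 3.02 on 42 df, power 90.7%.

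The stated 22 per group reproduces. It concerns the primary outcome only.

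**2. What is specified at each contact.**

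| Contact | Motor block | Other adverse effects |
|---|---|---|
| PACU | degree (4.4) | none stated |
| Phase 2 recovery | degree (4.4) | none stated |
| Diary and day 1 or 2 call | duration (4.6, 6.6) | none stated |
| 2-week contact | not named separately | named, without a list or definition |

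Motor block is covered at 3 of the 3 contacts before 2 weeks, and other adverse effects at 0 of 3. Sensory-block duration (4.6) touches on numbness, but the diary fields in 6.6 mention only motor block.

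**3. The cross-reference.** The 2-week contact is meant to supplement an initial data collection. Sections 6.2, 6.5 and the first part of 6.6 are the places where that collection would be described, and none mentions adverse events.

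**4. What 25 per arm can show.** The rates below are assumptions. Power is for two-sided Fisher at 0.05: the sum of Bin(i; 25, p₁) × Bin(j; 25, p₂) over outcomes with p ≤ 0.05 and more events in the sciatic arm. The last column assumes that half of the events are captured in each arm, for example 20% and 5% becoming 10% and 2.5%.

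| Sciatic vs IPACK | Full capture | Half captured |
|---|---|---|
| 20% vs 5% | 19.8% | 2.1% |
| 30% vs 10% | 30.5% | 7.2% |
| 40% vs 10% | 59.1% | 19.8% |

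Even full capture gives a descriptive comparison. Incomplete capture removes most of what remains.

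**The case against.** A reader might infer that the plan collects no adverse effects until 2 weeks. The documents do not support that. Motor blockade is the only adverse effect that 2.2 names, 2.3 singles it out, and it is recorded prospectively at every earlier contact. The motor-block comparison does not depend on recall at 2 weeks.

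Nor do the documents show that nothing else would be noted early, or that the 2-week contact is unstructured. The wording of 6.6 implies some earlier detection, and no checklist is either described or ruled out. Section 6.2 also records medications, admission status and discharge destination, which could reflect some treated or serious events. These points stand against the wider reading. They do not supply a definition, an endpoint or a collection time for the other effects.

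Two further points have force. The effects in 15.1 are attributed to ropivacaine, and both arms have the same drug, concentration, volume limit and mg/kg cap (6.3), so the documents give no reason to expect those effects to separate the arms. Blocks are placed under general anaesthesia (6.1), so patients could not report symptoms at injection. Both argue for a checklist that is limited to what patients can report after waking and that adds persisting numbness or weakness. They do not justify leaving out the question, because 2.2 claims a difference in adverse effects generally.

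**Conclusion.** The concern holds for adverse effects other than motor blockade. They are undefined, have no endpoint, no 6.2 data item, no diary field and no stated early-call content, and are named only at the 2-week contact. As written, that part of 2.2 cannot be answered reliably, and a general claim of fewer adverse effects could rest on motor block alone.

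The under-recording rests on an assumption: that effects such as prickling and drowsiness are short-lived and poorly recalled at about day 14. Section 15.1 gives no timing beyond the wearing-off of the block. The extent cannot be calculated from the documents.

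It would be too strong to infer that the trial can give no adverse-effect results by arm. Motor-block data will be available, although no cut-off turns degree or duration into an incidence. The primary comparison and its sample size are unaffected. The change should be made, but the trial's main conclusion does not depend on it.

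**What to change.** - Add to 4.0 an endpoint for the incidence of adverse effects other than motor block, by arm, reported separately from motor block.
- Compare it with the chi-square or Fisher's exact test already provided in 17.1, and state that with about 25 per arm the comparison is descriptive.
- Collect it with one fixed checklist, worded identically in both arms, covering at least the patient-reportable effects in 15.1 plus persisting numbness or weakness.
- Complete the checklist before PACU/phase 2 discharge, at the existing day 1 or 2 call and at the existing 2-week contact. Amend 6.2, 6.5 and 6.6 so that the initial data collection for adverse events is described.

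The cost is a wording amendment, a few minutes per contact, and a higher recorded event count in both arms because events are solicited. No visits are added and the sample size does not change.
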